5.4 Other evaluations

Pharmacokinetic (PK) Procedures: Venous blood samples will be collected for determination of plasmatic ezogabine concentrations at the primary outcome visit (V5). Drug concentrations will be used to determine protocol adherence, inclusion in the planned per-protocol analysis and to examine PK – pharmacodynamic (PD) relationships. Plasmatic ezogabine levels will be used to determine drug concentration.

6 SUBJECT SELECTION

6.1 Study Population

Subjects who will meet DSM-5 criteria for depressive disorder (MDD, persistent depressive disorder, other specified depressive disorder), clinically significant anhedonia (SHAPS \geq 20)

and at least moderate current illness severity (Clinical Global Impression–Severity [CGI-S] Scale ≥ 4) at the time of screening meeting all study inclusion and exclusion criteria will be eligible for participation in this study.

Recruitment feasibility: The research plan calls for the randomization of $n=48$ patients ages 18-65 with a primary diagnosis of current depressive disorder and significant anhedonia across the two performance sites (ISMMS and BCM) over a 20-month recruitment period, which is 1.2 patients randomized per month per site. This is a feasible goal based on current patient flow at the two sites, and our demonstrated track record of enrollment at similar rates in prior studies recruiting from similar populations.

6.2 Inclusion Criteria

1. Written informed consent obtained from subject and ability for subject to comply with the requirements of the study;
2. Men and women, age 18-65;
3. Participants must meet DSM-5 criteria for current depressive disorder (major depressive disorder [MDD], persistent depressive disorder, other specified depressive disorder) as determined by a study psychiatrist and confirmed using the Structured Clinical Interview for DSM-5 Research Version (SCID-5-RV);
4. Clinically significant anhedonia as determined by a SHAPS score ≥ 20 at screening;
5. Current illness severity is at least moderate, defined as a score of ≥ 4 on the Clinical Global Impression–Severity (CGI-S) Scale;
6. If female of childbearing potential, must agree to use of a medically accepted form of contraception, or else agree to abstinence.

6.3 Exclusion Criteria

1. A primary psychiatric diagnosis other than a depressive disorder as defined by DSM-5; [co-morbid anxiety disorders (including agoraphobia, generalized anxiety disorder, social anxiety disorder and panic disorder) and Posttraumatic Stress Disorder (PTSD) are allowed];
2. Diagnosis of a major cognitive disorder or evidence of cognitive impairment as assessed by a score of the Mini Mental Status Exam (MMSE) of <24 ;
3. Meets criteria for a substance or alcohol use disorder in the past 6 months;
4. Suicidal ideation with any intent or plan as measured by a Columbia Suicide Severity Rating Scale [C-SSRS] score of greater than 3 during the past month at the time of screening;
5. Female participants who are pregnant, breastfeeding, or may become pregnant, or unwilling to practice birth control during participation in the study;
6. Positive urine toxicology screen for drugs of abuse at the time of screening*;
7. Inability to swallow capsules;

8. Any unstable medical illnesses including hepatic, renal, gastroenterologic, respiratory, cardiovascular (including ischemic heart disease), endocrinologic, neurologic, immunologic, or hematologic disease;
9. Clinically significant abnormalities of laboratory tests, physical examination, or ECG;
10. Positive Hepatitis B surface antigen (HBsAg) and/or Hepatitis C Anti-Hepatitis C virus (HCV) antibody†
11. Moderate to severe renal insufficiency at the time of screening or at any point throughout study participation;
12. Prolonged QT Interval at screening, operationalized as a QTc of > 480 ms;
13. History of abnormal QT prolongation or congenital QT syndrome;
14. Concomitant use of a medication with a known significant risk of QT prolongation;
15. A history of retinal abnormalities (i.e., pigment changes, retinal dystrophy) or findings of retinal pathology on ophthalmological exam at baseline;
16. Presence of a condition or abnormality that in the opinion of the Investigator would compromise the safety of the patient or the quality of the data;
17. Use of any dis-allowed medication according to the study protocol**;
18. Serious and imminent risk of self-harm or violence as determined by the PI;
19. Extreme illness severity as defined by a GCI-S score >6;
20. Any contraindication to MRI including claustrophobia, any trauma or surgery which may have left magnetic material in the body, magnetic implants or pacemakers, and inability to lie still for 1 hour or more;
21. History of non-response to electroconvulsive therapy in the current depressive episode

** Exceptions:*

- a) Subjects with a positive urine drug screen for cannabinoids, barbiturates, opiates, amphetamines, or benzodiazepines may be allowed in the study provided that the drug was used for a documented, legitimate medical purpose and/or the use of such products may be discontinued (documented by a negative repeat test) prior to randomization; Subjects with a positive urine drug screen for drugs of abuse at any study visit following the randomization visit (e.g. V5 or V8) will not be discontinued from the study.*
- b) Medically appropriate episodic use (up to 3 days) of narcotic analgesics for acute medical indications is allowed (Discussion with PI required)*

*** Potential participants will not be discontinued from medication for the purposes of this study. If a patient is taking a protocol dis-allowed medication at the time of screening, the patient may discontinue the medication under the supervision of their treating physician in the case that the patient is not benefiting from the medication or otherwise wishes to discontinue the medication. In no case will a dis-allowed medication be discontinued for the purpose of study participation if the patient is receiving clinical benefit from the medication.*

† Subjects who will test positive for Hepatitis B or C at the time of the screening will not be allowed to participate in the study. If a subject tests positive for Hepatitis B or C, the study physician will inform the participant and provide a referral for medical evaluation and treatment as appropriate.

7 CONCURRENT MEDICATIONS

All subjects should be maintained on the same medications throughout the entire study period, as medically feasible, with no introduction of new chronic therapies. Refer to Table 1 for list of prohibited medications during the study.

7.1 Allowed Medications and Treatments

Study subjects are required to be free of antidepressant and other dis-allowed medication with CNS activity for a duration equivalent to 5 half-lives of the medication at the time of randomization. As needed (e.g., "PRN") use of non-benzodiazepine hypnotic agents (including zolpidem, zaleplon, eszopiclone, diphenhydramine, suvorexant, and ramelteon) or benzodiazepines not in excess of the equivalent of 2 mg of lorazepam daily will be allowed. Subjects will be prohibited from taking as needed benzodiazepines or other as needed therapy with CNS activity on the day of study assessments. Subjects receiving psychotherapy may continue to receive psychotherapy provided this therapy has been stable in terms of frequency for at least 2 months prior to screening and is expected to remain unchanged during the study treatment period.

7.2 Prohibited Medications and Treatments

A list of medications prohibited during the study is provided in Table 1 ("List of Prohibited Medications"). The administration of the cited drugs will be considered a protocol violation. In general, the following classes of medication are prohibited: (1) antidepressants, (2) antipsychotics, (3) anticonvulsants/mood stabilizers, (4) lithium, and (5) stimulants. In addition, concomitant use of a medication with a known significant risk of QT prolongation is prohibited.

8 STUDY TREATMENTS

8.1 Method of Assigning Subjects to Treatment Groups

Central randomization will be implemented in this study by the coordinating site. Forty-eight eligible patients will be randomly assigned to ezogabine (900 mg/day; n=24) or placebo treatment (n=24) groups in a 1:1 ratio using a computer-generated randomization scheme developed by the coordinating site. The randomization will be balanced by using randomly permuted blocks. The interactive web response system (IWRS) will assign a unique treatment code, which will dictate the treatment assignment and matching study drug kit for the subject.

8.2 Blinding

Patients who meet all entry criteria will be randomly assigned to one of the treatment arms, and assigned randomization numbers in consecutive order. The randomization list will be a computer-generated random-number list generated by the research pharmacist (who has no patient contact) at the coordinating site using a permuted block procedure. The randomization list will be provided by the research pharmacist at the coordinating site to the research pharmacist at the collaboration site. Due to the objective of the study, the identity of test and control treatments will not be known to investigators, research staff, or patients.

The following study procedures will be in place to ensure double-blind administration of study treatments:

- Access to the randomization code will be strictly controlled;
- Packaging and labeling of test and control treatments will be identical to maintain the blind;
- Investigators, study coordinators and all study personnel with study patient contact will remain blind to the treatment assignment.

The study blind will be broken on completion of the clinical study and after the study database has been locked. During the study, the blind may be broken by the research pharmacist **only** in emergencies when knowledge of the patient's treatment group is necessary for further patient management.

8.3 Test and Control Formulation

8.3.1 Formulation of Test Product

Ezogabine (Potiga[®], GlaxoSmithKline) is approved by the FDA for the adjunctive treatment of partial-onset seizures in patients aged 18 years and older. Ezogabine is produced by GlaxoSmithKline and supplied as film-coated immediate-release tablets for oral administration: 50 mg, purple, round, film-coated tablets debossed with "RTG 50" on one side; 200 mg, yellow, oblong, film-coated tablets debossed with "RTG-200" on one side; 300 mg, green, oblong, film-coated tablets debossed with "RTG-300" on one side; and 400 mg, purple, oblong, film-coated tablets debossed with "RTG-400" on one side. The tablets should be swallowed whole. The study drug will be formulated and manufactured according to currently established commercial production standards.

8.3.2 Formulation of Control Product

A placebo tablet for oral administration will be provided by the Investigational Drug Service at each site ready for administration in a drug case labeled with the required FDA warning statement, the protocol number, a treatment number, the name of the Sponsor, and directions for patient use and storage. The placebo product used in this study will be manufactured according to GMP and will contain inert substances. The research pharmacist at ISMMS will centrally randomize participants at all performance sites.

8.3.3 Packaging and Labeling

Packaging: Study drug will be supplied in a drug case at the research pharmacy at each site in the dosage prescribed by the PI or his designee (another study M.D. approved by the PI and the Institutional Review Board [IRB] for this role).

Labeling: Each drug case of study drug will be labeled with the required FDA warning statement, the protocol number, a treatment number, the name of the Sponsor, and directions for patient use and storage

8.4 Supply of Study Medication at the Site

Ezogabine will be purchased by the research pharmacy at each site by an appropriate wholesale drug company. The Investigational Drug Service at ISMMS purchases ezogabine for research purposes from Amerisource-Bergen Corporation, based in Chesterbrook, Pennsylvania. The initial study drug shipment will be shipped after site activation. Subsequent study drug shipments will be made after site request for resupply.

8.4.1 Dosage/Dosage Regimen

Titration Period. Study drug titration will follow the guidelines contained within the FDA package insert and will not exceed the maximum approved dose for partial-onset seizures (1,200 mg daily). For this study, a daily dose of 900 mg has been selected, along with placebo.

For the ezogabine arm, participants start at 100 mg 3 times daily (300 mg per day) and increase at weekly intervals by 150 mg (50 mg 3 times per day) up to a stable dosage of 900 mg daily. A 150 mg increase each week is the maximum increase recommended by the FDA. Those assigned to receive placebo will receive capsules containing an inactive compound at a frequency comparable to those in active treatment (i.e., 1 capsule, 3 times per day). Dose titration will be conducted based on subject tolerability.

Subjects who are unable to tolerate a protocol-specified dose increase will be retained in the study at the highest tolerated dose for that subject through to the Primary Outcome Visit (V5), before beginning to taper off of the medication. In the event that a subject experiences a potential dose-dependent adverse medication effect in the opinion of the investigator, the subject will be maintained at the subject's highest previously tolerated dose. One dose reduction for the purpose of resolving suspected medication-related adverse effects will be allowed per subject. Subjects who continue to experience tolerability issues despite the dose reduction will initiate the taper phase and will be exited early from the study protocol. The taper schedule will follow procedures reported in section 10.5 "Taper Period" and section 10.6 "Study Exit Visit" (Visit 6) and early withdrawal". All available data for each subject will be included in the statistical analyses, including from subjects who discontinue early for any reason. Study subjects who discontinue early for any reason, however, will not be replaced. During the trial, the following dosages of ezogabine will be used: 50 mg, 200 mg and 300 mg. To assure the blindness of the trial, the research pharmacist at each site will encapsulate every pill so that all study pills regardless of dosage will look identical.

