8.6 Measures of Treatment Compliance

Subsequent to randomization, study participants are provided with study drug or placebo in identical packaging and sufficient medication to reach the next visit is dispensed (plus a few extra days supply to account for scheduling and related issues). Adherence to study medication will be measured throughout the study using pill count, patient diary, subject report, and drug plasmatic levels. Subjects will be asked to keep a patient diary noting the date and time they take the study drug and any adverse effects. They will be asked to bring their patient diary to each study visit along with all used and unused study drug containers. Compliance monitoring by pill counting will occur at each study visit: pills will be returned for pill counting in the study drug containers. A study team member will count the number of returned pills and record the number on the "Pill tracking log". Venous blood samples will be collected for determination of plasmatic ezogabine concentrations at the time point

specified and will be summarized by visit. Drug concentrations will be used to determine protocol adherence, inclusion in the planned per-protocol analysis and to examine PK and PD relationships.

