4. EKG*
5. Perform self and clinician administered ratings scale:
 - SHAPS
 - TEPS
 - ACIPS
 - SLIPS
 - QIDS-SR
 - MADRS
 - CSSRS
 - CGI-S
 - CGI-I

Note: Study Visits 1, 2, 3, and 4 are due to take place 1, 2, 3, and 4 weeks after the Baseline/Randomization Visit (Visit 0) respectively. To allow for scheduling feasibility, Visits 1-4 can take place within 3 days before or after the scheduled visit.

** During the Double Blind Treatment Period (Visits 1 – 4), EKG will occur only on visit 4, when participants reach drug exposure of 750 mg daily over the prior week and are poised to escalate to the highest dose tested in the study of 900 mg daily. The additional EKG screening at visit 4 will ensure that no adverse QT effects have emerged prior to escalating to the highest dose. If a subject will show a QT intervals over 500 milliseconds or a 60-milliseconds increase in the QT interval from baseline, the dose will not be escalated and the subject will be tapered down from study medication over a three-week period. The study participant will be asked to return to study site to complete the primary outcome*

assessment after one week and will be exited from study upon completion of the taper period. Please, refer to section 10.6 Study exit Visit (Visit) and early withdrawal.

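### Protocol 8.4.1 contradicts itself on capsule number: one capsule three times a day fits only two of the five titration steps, and nothing states that the count is equal in both arms

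*Protocol*

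**What the plan says.** Four statements in protocol section 8.4.1 bear on the number of capsules.

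- **Schedule.** On ezogabine, "participants start at 100 mg 3 times daily (300 mg per day", and then "increase at weekly intervals by 150 mg (50 mg 3 times per day) up to a stable dosage of 900 mg daily". Section 10.3 agrees with this schedule: "EKG will occur only on visit 4, when participants reach drug exposure of 750 mg daily over the prior week".
- **Strengths.** During the trial "the following dosages of ezogabine will be used: 50 mg, 200 mg and 300 mg".
- **Encapsulation.** To protect the blind, "the research pharmacist at each site will encapsulate every pill so that all study pills regardless of dosage will look identical".
- **Placebo.** Inactive capsules are given "at a frequency comparable to those in active treatment (i.e., 1 capsule, 3 times per day".

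Other sections deal with appearance and packaging. Section 8.2 requires matching packaging and labels, and requires everyone with patient contact to stay blind. Section 8.4.2 repeats that drug and placebo are encapsulated to look alike, and says that only the site pharmacist knows what the pills are. Section 8.6 provides for identical packaging and for a pill count at each visit: "A study team member will count the number of returned pills and record the number on the" pill tracking log. SAP section 5.3.2 defines compliance from the number and percentage of prescribed pills taken and compares it by arm.

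No section says that the number of capsules per intake is the same in both arms, that filler capsules are added, or that several tablets go into one capsule.

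**The concern.** Capsules that look alike protect the blind only if their number is also alike. Followed literally, the placebo count and the encapsulation rule give different numbers of capsules in the two arms at some steps. The number would be visible to patients, who take the capsules and keep a diary, and to the team member who counts returns and is meant to stay blind.

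Most secondary outcomes are self-report or clinician ratings, which expectation can move. The primary outcome, ventral striatal activation in a monetary incentive task, is less subjective but still depends on engagement with the task. SAP section 3.1 makes it the only go/no-go criterion. The compliance comparison is also affected, because the count of prescribed pills is its denominator.

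**Working it through.** **Inputs.** Daily doses over the five steps: 300, 450, 600, 750 and 900 mg (8.4.1; the fourth step is confirmed in 10.3). Intakes per day: 3 (8.4.1). Pill strengths: 50, 200 and 300 mg (8.4.1). Tablets are taken whole (8.3.1). Stated count: 1 capsule per intake.

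**Formulae.** Dose per intake = daily dose / 3. Fewest pills k = smallest number of whole pills from {50, 200, 300} mg that adds up exactly to that dose. Capsules per 7 days = k × 3 × 7 = 21k, with one pill per capsule.

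| Step | Daily dose (mg) | Per intake (mg) | Fewest pills k | Ezogabine capsules per 7 days | At 1 capsule per intake |
|---|---|---|---|---|---|
| 1 | 300 | 100 | 2 (50+50) | 42 | 21 |
| 2 | 450 | 150 | 3 (50+50+50) | 63 | 21 |
| 3 | 600 | 200 | 1 | 21 | 21 |
| 4 | 750 | 250 | 2 (200+50) | 42 | 21 |
| 5 | 900 | 300 | 1 | 21 | 21 |

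The stated figure of one capsule is therefore reproduced at steps 3 and 5 only, which is 2 of 5. At the other 3 of 5 it is not.

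**Illustrative total.** With full titration in exact 7-day steps, ezogabine takes 42 + 63 + 21 + 42 + 21 = 189 capsules. One capsule per intake gives 5 × 21 = 105.

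**Could other arrangements rescue the single capsule?**

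- *The 400 mg tablet.* Section 8.3.1 lists it as marketed, but it exceeds every per-intake dose, so k does not change.
- *Unequal intakes, three pills a day.* With the listed strengths, 300 = 50+50+200, 450 = 50+200+200, 600 = 3 × 200 and 900 = 3 × 300. No three pills make 750; the nearest totals are 200+200+300 = 700 and 200+300+300 = 800. Section 8.4.1 in any case states equal intakes for the starting dose and for each increment.
- *Several tablets in one capsule.* This would work arithmetically, but the protocol does not describe it.

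**Taper.** Section 10.5 gives daily totals of 750, 600 and 300 mg for a week each after 900 mg. It does not give the split by intake. Assuming three equal intakes, the doses are 250, 200 and 100 mg, so k = 2, 1 and 2. On that assumption one capsule does not fit in 2 of 3 taper weeks.

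**The case against.** The arithmetic is not in dispute; the reading is. The best case for the plan has four parts.

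1. **The placebo sentence asserts similarity.** Its i.e. explains what is comparable, so it can fairly be read as one capsule per intake in both arms. This stands as a possible reading. It does not remove the problem, because one capsule then has to hold up to three tablets, and the encapsulation sentence, which speaks of every pill, says nothing of the kind.
2. **The vocabulary is loose.** Placebo is a tablet in 8.3.2 and a capsule in 8.4.1, and 8.4.3 speaks of swallowing a whole tablet after encapsulation. A strict rule of one pill per capsule should not be hung on one noun. This also stands, and it is why the finding is that the statements conflict, not that the single-pill reading is the right one.
3. **Matching is clearly intended**, and pharmacy instructions that are not part of these documents may have secured it. That may be so. But each site's pharmacy does its own encapsulating, so a rule stated in the protocol is what would make them act alike.
4. **The impact is bounded.** The secondary outcomes are exploratory without formal tests (SAP 3.2, 5.1), and nothing in the documents quantifies an expectation effect on the imaging measure. This stands.

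A reader might go further and infer that placebo was held at one capsule for the whole study, that the arms did receive different counts, or that a changing count would identify ezogabine almost for certain. The documents do not support this. They do not say that the placebo count is fixed for the whole study, they do not record what was dispensed, and a patient who has not read the dosing section may not know what a changing count means.

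**Conclusion.** Wrong as written. The schedule, the strengths, the encapsulation rule and the single-capsule figure in section 8.4.1 cannot all be true: at least 2, 3, 1, 2 and 1 pills per intake are needed, and one capsule fits 2 of 5 steps. That result rests only on the stated equal intakes, listed strengths and whole tablets, with one pill per capsule.

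The consequence for the blind is conditional. If pills are encapsulated singly and placebo stays at one capsule, counts differ between arms at 3 of 5 titration steps, and in 2 of 3 taper weeks if the daily totals are split equally. If one capsule per intake is meant in both arms, the counts match but the protocol omits the filling rule that makes this possible.

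The totals of 189 and 105 are an illustration only. Section 8.4.1 allows dose holds and one reduction, and section 10 allows visit windows and 7 to 14 days at the highest tolerated dose, so real counts would vary. Unbound by any of this, the finding concerns the text of the plan; it is not evidence that unblinding occurred.

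**What to change.** Reconcile the statements on strengths, encapsulation and capsule number in sections 8.4.1 and 8.4.2. Replace the single-capsule parenthesis with a rule such as: *the number of capsules per intake is identical in both arms at every titration, dose-reduction and taper step.* Then say how this is achieved, by either of two routes:

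- placebo capsules matched one for one to the ezogabine capsules at each step; or
- all tablets of an intake filled into one capsule, with one capsule per intake in both arms.

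State in section 10.5 how the daily taper totals divide into intakes, so that the same rule can be applied there. The prescribed count used for compliance in SAP 5.3.2 then has the same basis in both arms.

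No dose changes. The cost is wording, pharmacy work and, for the first route, placebo capsules: 189 − 105 = 84 more per participant over a full titration in 7-day steps, or 84 × 24 = 2,016 for 24 placebo participants. The taper adds (2 + 1 + 2) × 21 − 3 × 21 = 42 per participant if intakes are equal. The second route needs no extra placebo capsules, but the pharmacies must confirm that up to three tablets fit in one capsule, which the documents do not address.
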